### 5.10.3.3 Specimen Receipt and Processing at the Mayo Clinic Cancer Center

Frozen plasma aliquots will be received at the Mayo Clinical Cancer Center. Upon receipt, plasma will be accessioned, barcoded, and stored in a -80°C freezer until distribution for testing.

### 5.10.3.4 Site(s) Performing Correlative Study

Samples will be analyzed in the Pharmacology Core of the Mayo Clinic Cancer Center, which has developed validated assays for over 85 separate anticancer drugs during the course of its existence. This assay will be performed under the direction of [name].

## 5.10.4 Osimertinib (AZD9291) Pharmacokinetics

### 5.10.4.1 Hypothesis and Rationale

Osimertinib (AZD9291) is a moderate inhibitor of BCRP and Telaglenastat (CB-839) HCl is a substrate of efflux pumps. Therefore, the most likely drug interaction is increased plasma concentration of Telaglenastat (CB-839) HCl. However, since both drugs are orally administered, an impact on Osimertinib (AZD9291) pharmacokinetics cannot be ruled out without pharmacokinetic studies. The primary endpoint will be comparing the AUC0-8hr in this study to a prior ETCTN single agent Osimertinib (AZD9291) study (9903). Css concentrations

NCI Protocol #: 10216

Version Date: 09/17/2024

of Cycle 2 Day 1 and subsequent cycles will also be evaluated as potential biomarkers of efficacy and toxicity.

#### 5.10.4.2 Assay Validity and Appropriateness for Study

LC/MS/MS is the analytical standard for quantitation of drug plasma concentrations due to its sensitivity and accuracy. A LC/MS/MS assay for the analysis of Osimertinib (AZD9291), AZ5104, and AZ7550 was developed and validated based on a previously published method (Rood *et al.*, 2016). Following SALLE extraction, samples were analyzed with a Shimadzu Nexera X2 series interfaced with a Sciex QTRAP® 6500+ MS/MS. Liquid chromatography was performed using a Waters® Acquity UPLC® BEH C8 column. MS/MS data was obtained in positive ion mode (ESI+) with Osimertinib (AZD9291) at m/z 500.118 → 72.092, AZ5104 at m/z 486.761 → 72.092, AZ7550 at m/z 486.761 → 430.178, and pazopanib at m/z 438.717 → 358.146.

Stock solutions of 100 mcg/mL of Osimertinib (AZD9291) were used to obtain nine validation samples in human heparin plasma (1000, 800, 500, 200, 100, 50, 3, and 1 ng/mL). Each sample was measured analytically on three separate days. The standard curve was linear from 1 – 1000 ng/mL,  $R^2 = 0.987$  with an inter-day variability of 3.74% for high standard (1000 ng/mL),  $n = 3$  and 12.46% for low standard (1 ng/mL),  $n = 3$  over three days. The lower limit of quantification (LLOQ) was 3 ng/mL and limit of detection (LOD) was 1 ng/mL.

We will use a validated LC/MS/MS assay for the analysis of Osimertinib (AZD9291) and metabolites analysis. As these are blood samples, obtaining the samples represents minimal risk however, careful consideration to patient inconvenience for sample collection was conducted. Given the large body of Osimertinib (AZD9291) PK information and the small likelihood of a drug interaction effecting Osimertinib (AZD9291) plasma concentrations, as described above, the  $AUC_{0-8hr}$  will be used as the primary endpoint, to minimize subject sampling burden.

#### 5.10.4.3 Specimen Receipt and Processing at the Ohio State University

Frozen plasma aliquots will be received at the Ohio State University. Upon receipt, plasma will be accessioned, barcoded, and stored in a -80°C freezer until distribution for testing.

## 5.11 Exploratory/Ancillary Correlative Studies

### 5.11.1 Whole Exome Sequencing / RNA sequencing

In order to determine possible biomarkers for response to treatment with Osimertinib (AZD9291) and Telaglenastat (CB-839) HCl, WES and RNA sequencing will be performed on the archival/baseline tumor specimen. Recent studies have demonstrated the importance of co-mutations in *EGFR*-mutated NSCLC, and potential primary resistance mechanisms to Osimertinib (AZD9291) have been elucidated, including regulators of cell cycle such as *CDK4/6* (Blakely *et al.*, 2017) as well as additional *EGFR* mutations L718 and L792 (Yang *et al.*, 2018). Evaluation for these and other mutations at baseline will be performed to identify biomarkers associated with drug activity

#### 5.11.1.1 Specimen Receipt and Processing at the EET Biobank

Archival formalin-fixed paraffin-embedded tissue (block or slides) will be used for this assay. If a block is received, then the EET Biobank will cut and H&E stain slides. A pathology quality control review to assess tumor content and annotate slides for macrodissection will be completed for all tissue received. Unstained slides will be macrodissected, if needed, and scraped for DNA and RNA co-extraction. DNA will be banked in a stock vial and RNA will be divided into 5 aliquots; all nucleic acids will be stored in a -80°C freezer until distribution for testing.

Any additional FFPE tissue blocks or slides will be banked at room temperature.

DNA will be extracted from blood collected in cfDNA Streck tubes at the baseline time point, following plasma processing. DNA will be stored in a -80°C freezer until distribution for testing.

#### 5.11.1.2 Site(s) Performing Correlative Study

WES and RNAseq will be performed on archival samples by the MoCha, Frederick National Laboratory for Cancer Research (FNLCR) under the supervision of [name]. ([[contact]](mailto:[contact])).

## 5.11.2 Cell-Free DNA Analysis

Peripheral blood will be collected to assess cfDNA for *EGFR* mutational status, T790M mutational status, and resistance mechanisms. cfDNA for *EGFR* status will be compared with archival/baseline specimen for concordance. Blood based assays for detection of resistance mechanisms are widely used in clinical practice, and have also yielded information about resistance mechanisms to treatment (Blakely *et al.*, 2017).

### 5.11.2.1 Specimen Receipt and Processing at the EET Biobank

Blood received in cfDNA Streck tubes will be processed for plasma upon receipt at the EET Biobank. The baseline cfDNA Streck tube will also be processed for DNA (to be used for other correlative studies), and the buffy coat from other time points will also be processed and stored. Plasma will be stored in 1 mL aliquots in a -80°C freezer until distribution for testing. Buffy coat will also be stored in a -80°C freezer.

### 5.11.2.2 Site(s) Performing Correlative Study

This study will be performed at the MoCha, Frederick National Laboratory for Cancer Research (FNLCR) under the supervision of [name]. ([[contact]](mailto:[contact])).

## 6 TREATMENT PLAN

### 6.1 Agent Administration

Treatment will be administered on an outpatient basis. Reported AEs and potential risks are described in Section 10. Appropriate dose modifications are described in Section 7. No investigational or commercial agents or therapies other than those described below may be administered with the intent to treat the patient's malignancy.

**Dose Escalation Treatment Plan:** A single arm dose escalation portion of the study will first be performed to determine the optimal dosing strategy where three dose levels will be assessed. Extensive PK studies will also be conducted to assess for any potential drug-drug interactions through the obtaining of peripheral blood. Eligible patients will initially receive treatment with single agent Telaglenastat (CB-839) HCl BID according to the dose escalation strategy and PK sampling will be done on Day 15. Starting on Day 16, patients will then go on to receive both Osimertinib (AZD9291) 80 mg PO QD as well as Telaglenastat (CB-839) HCl PO BID at the same dose as initially provided during the monotherapy portion of the study and a second set of PK analyses will be conducted on Day 1 of Cycle 2 for both Osimertinib (AZD9291) and Telaglenastat (CB-839) HCl (see table below). Peripheral blood will also be obtained for a PK assessment at the beginning of each 28- day treatment cycle starting with Cycle 2. An assessment for response to treatment will be conducted with a CT of the chest, abdomen, and pelvis (C/A/P) every 2 months as is standard practice.

Patients will continue to receive treatment until the time of disease progression, unacceptable toxicity, or treatment is discontinued based on patient/physician preference.

Patients enrolled to the dose escalation portion of the study will be treated according to a dose escalation schedule where three different dose levels will be assessed. For all dose levels, the Osimertinib (AZD9291) dose will be set at 80 mg PO QD. The dose levels of Telaglenastat (CB-839) HCl are as follows:

1) 400 mg PO BID; 2) 600 mg PO BID; 3) 800 mg PO BID. Dose Level -1 will be 200 mg Telaglenastat (CB- 839) HCl BID.

Phase 1 Dose Escalation Schedule		
Dose Level	Dose*	
	Telaglenastat (CB-839) HCl (mg) orally BID	Osimertinib (AZD9291) (mg) orally daily
Level -1	200 mg	80 mg
Level 1 (Starting Dose)	400 mg	80 mg
Level 2	600 mg	80 mg
Level 3	800 mg	80 mg

BID = twice daily, QD = once daily  
\*Dosing is given orally on a continuous schedule

Regimen Description					
Agent	Premedications	Dose*	Route	Schedule	Cycle Length
Telaglenastat (CB-839) HCl	None	Varying** (400-800 mg, 2-4 tablets)	PO BID with food	Continuous	28 days (4 weeks)
Osimertinib (AZD9291)	None	80 mg (1 tablet)	PO QD	Phase 1: Continuous starting on C1D16  Phase 2: Continuous	

PO = by mouth, QD = once daily, BID = twice daily

\* *Dosing is given orally on a continuous schedule*

\*\**Doses as appropriate for assigned dose level.*

Expansion Cohort Treatment Plan: A 10-patient expansion cohort study will then be performed at the maximum tolerated dose (MTD) identified in the dose escalation study. Eligible patients will receive Osimertinib (AZD9291) 80 mg PO QD as well as Telaglenastat (CB-839) HCl PO BID at doses determined during the phase 1 portion of the study. An assessment for response to treatment will be conducted with a CT C/A/P every 2 months. Peripheral blood specimens will be collected at baseline, one-month post-treatment and at the time of RECIST progression to assess cfDNA for *EGFR* mutational status, T790M mutational status and *EGFR* resistance mechanisms as well as to assess changes in the metabolites glutamine, glutamate, aspartate and asparagine. Patients will continue with treatment until the time of disease progression, unacceptable toxicity, or treatment is discontinued based on patient/physician preference.

Patients enrolled to the expansion cohort of the study will be treated with Osimertinib (AZD9291) 80 mg PO QD as well as Telaglenastat (CB-839) HCl PO BID at 800mg BID which was evaluated in the dose escalation portion of the study and found to be safe. The initial dose of Osimertinib (AZD9291) 80 mg QD can be reduced to 40 mg QD for patients enrolled to the phase 2 study as detailed in Section 7. Patients will be treated until the time of disease progression, unacceptable toxicity, or treatment is discontinued per patient/physician preference. Patients will be followed for 30 days after completion of therapy unless treatment related toxicities have not resolved to grade 1 in which case they will be followed until toxicities have resolved to grade 1.

Patients will be requested to maintain a medication diary of each dose of medication. The medication diary (Appendix G) will be returned to clinic staff at the end of each course.

All protocol therapy with Telaglenastat (CB-839) will end on 2/28/25. The clinical supply of Telaglenastat will no longer be available after the terminal lot shelf life dating of 2/28/25 is reached. After that date, patients may remain on Osimertinib single agent at the investigator discretion until meeting other off therapy criteria.

#### 6.1.1 Telaglenastat (CB-839) HCl

When taken with food, Telaglenastat (CB-839) HCl has demonstrated a slightly higher (~1.3 fold) absorption, and patients have experienced significantly fewer incidences of elevated LFTs compared to the fasted state. Telaglenastat (CB-839) HCl should be taken with breakfast and dinner, roughly 12 hours apart.

#### 6.1.2 Osimertinib (AZD9291)

Based on the results from the definitive food effect study and supporting results from the exploratory study, it is recommended that Osimertinib (AZD9291) can be taken with or without food.

#### 6.1.3 Other Modalities or Procedures

N/A

## 6.2 **Definition of Dose-Limiting Toxicity**

The DLT period will be 28 days (of combined treatment) and patients will continue therapy until the time of disease progression, unacceptable toxicity, or per patient/physician preference. To be evaluable for a DLT, patients must have started the combination therapy portion of the study. Patients who complete the DLT period and receive at least 75% of scheduled days of treatment will be evaluable for safety endpoints. Patients who discontinue combined treatment during the 28-day evaluation period for any reason other than treatment-related or dose-limiting toxicity will not be evaluable. Non-evaluable patients will be replaced. A DLT will be defined as any AE that cannot be determined to be unrelated to study treatment, occurs within the first 28 days of combination treatment, and that meets at least one of the following criteria. Non-hematologic DLTs will be defined as grade 3 or higher toxicities according to the CTCAE version 5.0 except the following— grade 3 nausea, vomiting, or diarrhea lasting <48 hours and controlled by optimal antiemetic/antidiarrheal therapy; clinical laboratory abnormalities that are reversible to  $\leq$ grade 1 or baseline status within 72 hours with outpatient care and/or monitoring or that are not considered clinically significant by the PI. Grade 3 rash attributed to the combination will be considered a DLT if grade 3 despite maximal medical management (including oral antibiotic, topical or oral steroids) for >72 hours. Hematologic DLTs will be defined as the following— grade 4 or higher neutropenia [absolute neutrophil count (ANC)  $< 0.5 \times 10^9/L$ ]; grade 3 or higher febrile neutropenia (ANC  $< 1.0 \times 10^9/L$  with a fever  $\geq 38.3^{\circ}\text{C}$ ); grade 4 or higher thrombocytopenia ( $< 25.0 \times 10^9/L$ ); and grade 3 or higher thrombocytopenia associated with grade 3 or higher bleeding. Patients will be followed for 30 days after completion of therapy unless treatment-related toxicities have not resolved to grade 1 in which case they will be followed until toxicities have resolved to grade 1. Any grade of pneumonitis will also be considered a DLT.

Dose escalation will proceed within each cohort according to the following scheme. DLT is defined above.

Number of Patients with DLT at a Given Dose Level	Escalation Decision Rule
0 out of 3	Enter 3 patients at the next dose level.
$\geq 2$	Dose escalation will be stopped. This dose level will be declared the maximally administered dose (highest dose administered). Three (3) additional patients will be entered at the next lowest dose level if only 3 patients were treated previously at that dose.
1 out of 3	Enter at least 3 more patients at this dose level. 

• If 0 of these 3 patients experience DLT, proceed to the next dose level.

• If 1 or more of this group suffer DLT, then dose escalation is stopped, and this dose is declared the maximally administered dose. Three (3) additional patients will be entered at the next lowest dose level if only 3 patients were treated previously at that dose.

$\leq 1$ out of 6 at highest dose level below the maximally administered dose	This is generally the RP2D. At least 6 patients must be entered at the RP2D.

### 6.3 General Concomitant Medication and Supportive Care Guidelines

Because there is a potential for interaction of Telaglenastat (CB-839) HCl and Osimertinib (AZD9291) with other concomitantly administered drugs, the Case Report Form (CRF) must capture the concurrent use of all other drugs, over-the-counter medications, or alternative therapies. The PI should be alerted if the patient is taking any agent known to affect or with the potential for drug interactions. The potential targets for drug interaction can involve, but are not limited to CYP450, glucuronidation, P-glycoprotein, protein binding, or reduced absorption from proton-pump inhibitors. Check the study agent Investigator's Brochure for potential sources of drug interactions. The study team should check a frequently-updated medical reference for a list of drugs to avoid or minimize use of. Appendix B (Patient Drug Information Handout and Wallet Card) should be provided to patients if available, and Appendix D (Guidance Regarding Potential Interactions with Concomitant Medications) for additional information on concurrent medications.

#### 6.3.1 Radiotherapy

Radiotherapy will be permitted if deemed clinically beneficial by the treating physician for palliation of painful bone disease or in cases of symptomatic CNS disease amenable to stereotactic radiation. Whole brain radiation and radiation of target lesions is not permitted. Study treatment should be held for 3 days before and after radiotherapy.

#### 6.3.2 Osimertinib (AZD9291), CYP 3A4 and BCRP

NCI Protocol #: 10216

Version Date: 09/17/2024

Because there is a potential for interaction of Osimertinib (AZD9291) with other concomitantly administered drugs, the CRF must capture the concurrent use of all other drugs, over-the-counter medications, or alternative therapies. The PI should be alerted if the patient is taking any agent known to affect or with the potential for drug interactions. *In vitro* studies demonstrate that Osimertinib (AZD9291) and its active metabolites are primarily metabolized by CYP 3A4 enzymes. Potent inducers of CYP 3A4 are therefore contraindicated and a wash-out period is required (duration of wash-out varies, See Appendix D [Guidance Regarding Potential Interactions With Concomitant Medications]).

Patients taking rosuvastatin should have creatine phosphokinase levels monitored (due to BCRP-mediated increase in exposure). If the patient experiences any potentially relevant AEs suggestive of muscle toxicity including unexplained muscle pain, tenderness, or weakness, particularly if accompanied by malaise or fever, rosuvastatin must be stopped and any appropriate further management should be taken.

### **6.3.3 Telaglenastat (CB-839) HCl and CYP2C9**

Telaglenastat (CB-839) HCl is metabolized by human hepatocytes primarily through amide hydrolysis. Telaglenastat (CB-839) HCl does not appear to induce CYP drug-metabolizing enzymes and only weakly inhibits CYP2C9 (~40-50% inhibition at 5 mcM) *in vitro*. Although Telaglenastat (CB-839) HCl is not expected to inhibit CYP2C9 at the exposure levels planned, caution is warranted when administering Telaglenastat (CB-839) HCl to patients taking drugs that are highly dependent on CYP2C9 for metabolism and have a narrow therapeutic index. A list of medications that are CYP2C9 substrates is provided in Appendix C (Cytochrome P450 [CYP] 2C9 Substrates).

### **6.3.4 Telaglenastat (CB-839) HCl and Proton Pump Inhibitors**

Preliminary PK data generated in single agent phase 1 studies indicate that concomitant use of PPIs may reduce absorption of Telaglenastat (CB-839) HCl, resulting in decreased systemic exposure. Although patients are not required to discontinue their use of these agents, the strong preference is for patients to discontinue PPIs prior to joining the study. Antagonists of the H2 histamine receptor (*e.g.*, ranitidine, famotidine, *etc.*) may be substituted for PPIs. For patients unable to discontinue PPI therapy or that require restarting PPI therapy while on study, administration of Telaglenastat (CB-839) HCl with an acidic beverage (*e.g.*, orange juice) or supplement (*e.g.*, citric acid) may be an option. If an acidic beverage/oral supplement is administered along with the Telaglenastat (CB-839) HCl dose, it should be recorded on the appropriate electronic CRF (eCRF), including the identity of the beverage/supplement, dosage, and start and stop dates of administration.

To aid absorption, it is recommended that Telaglenastat (CB-839) HCl is taken at least 2 hours before or at least 10 hours after H2 receptor agonist therapy, or at least 2 hours before or at least 2 hours after other antacid therapy.

## **6.4 Duration of Therapy**

NCI Protocol #: 10216

Version Date: 09/17/2024

In the absence of treatment delays due to AE(s), treatment may continue until one of the following criteria applies:

- Disease progression
- Intercurrent illness that prevents further administration of treatment
- Unacceptable AE(s)
- Patient decides to withdraw from the study
- General or specific changes in the patient's condition render the patient unacceptable for further treatment in the judgment of the investigator
- Clinical progression
- Patient non-compliance
- Pregnancy
  - All women of child bearing potential should be instructed to contact the investigator immediately if they suspect they might be pregnant (e.g., missed or late menstrual period) at any time during study participation.
  - The investigator must immediately notify CTEP in the event of a confirmed pregnancy in a patient participating in the study.
- Termination of the study by sponsor
- The drug manufacturer can no longer provide the study agent

The reason(s) for protocol therapy discontinuation, the reason(s) for study removal, and the corresponding dates must be documented in the CRF.

## **6.5 Duration of Follow-Up**

Patients will be followed for 30 days after removal from study or until death, whichever occurs first. Patients removed from study for unacceptable AE(s) will be followed until resolution or stabilization of the AE.

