All toxicities will be summarized as the percentage of patients experiencing each type and grade of event according to dose level. Patients who receive at least one dose of treatment will be included in the analysis.

The ORR will be calculated as the proportion of patients who achieve a response to therapy divided by the total number of evaluable patients. An evaluable patient is defined as an eligible patient who has received at least one dose of therapy and has centralized confirmation of positive *EGFR* mutation status. All evaluable patients will be included in calculating the ORR for the study along with corresponding 95% binomial CIs (assuming that the number of patients who respond is binomially distributed). Separately, all patients treated at the RP2D in either the dose expansion or the expansion cohort will be analyzed.

Definition of Primary Endpoints

- Safety, tolerability and RP2D of combination therapy with Telaglenastat (CB-839) HCl and Osimertinib (AZD9291) in patients with metastatic *EGFR* activating mutation positive NSCLC.

Definition of Secondary Endpoints

- DLTs as assessed by CTCAE version 5.0 of the combination of Telaglenastat (CB-839) HCl and Osimertinib (AZD9291) in patients with metastatic *EGFR* activating mutation positive NSCLC.
- PFS of patients with metastatic *EGFR* activating mutation positive NSCLC who have progressed on front-line *EGFR* inhibitor therapy following treatment with Telaglenastat (CB-839) HCl and Osimertinib (AZD9291). PFS is defined as the time from initiation of therapy to documented progression or death without progression.
- OS of patients with metastatic *EGFR* activating mutation positive NSCLC who have progressed on front-line *EGFR* inhibitor therapy following treatment with Telaglenastat (CB-839) HCl and Osimertinib (AZD9291). OS is defined as the time from initiation of therapy to death from any cause.

Definition of Correlative Endpoints

- Post-Telaglenastat (CB-839) HCl PK as assessed by Telaglenastat (CB-839) HCl drug levels following both single agent therapy as well as combination therapy with Telaglenastat (CB-839) HCl and Osimertinib (AZD9291) in patients with metastatic *EGFR* activating mutation positive NSCLC.
- Post-Osimertinib (AZD9291) PK as assessed by Osimertinib (AZD9291) drug levels following combination therapy with Telaglenastat (CB-839) HCl and Osimertinib (AZD9291) in patients with metastatic *EGFR* activating mutation positive NSCLC.  

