### 9.4 Analysis of Secondary and Exploratory Endpoints

Frequency and severity of AEs and tolerability of the regimen will be collected and summarized by descriptive statistics. The maximum grade for each type of toxicity will be recorded for each patient, and frequency tables will be reviewed to determine toxicity patterns. All patients who have received at least one dose of the therapeutic agents will be evaluable for toxicity and tolerability.

We will explore PK endpoints such as  $C_{ss}$ , AUC,  $C_L$ ,  $V_d$ , and  $t_{1/2}$  computed using non-compartmental and compartmental methods. We will use graphical analyses as well as repeated measure models (linear or nonlinear mixed models, generalized estimating equations [GEE]) to assess the PK and PD markers described above in relation to clinical treatment outcomes, recognizing some inherent limitations due to sample size.

OS will be defined as time from initiation of therapy to death. PFS will be defined as the time from initiation of therapy to the time of RECIST progression or death. Survival will initially be modeled using Kaplan-Meier methods, resulting in median survival times with 95% CI, assuming sufficient events have occurred.

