### 10.3.2 Expedited Reporting Guidelines

Use the NCI protocol number and the protocol-specific patient ID assigned during trial registration on all reports.

**Note: A death on study requires both routine and expedited reporting, regardless of causality. Attribution to treatment or other cause must be provided.**

Death due to PD should be reported as **Grade 5 “Disease Progression”** under the system organ class (SOC) “General disorders and administration site conditions.” Evidence that the death was a manifestation of underlying disease (e.g., radiological changes suggesting tumor growth or progression; clinical deterioration associated with a disease process) should be submitted.

**Phase 1 and Early Phase 2 Studies: Expedited Reporting Requirements for Adverse Events that Occur on Studies under an IND/IDE within 30 Days of the Last Administration of the Investigational Agent/Intervention**

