#### Expedited AE reporting timeframes are defined as:

- “24-Hour notification, 5 Calendar Days” - The SAE must initially be reported via CTEP-AERS within 24 hours of learning of the SAE, followed by a complete expedited report within 5 calendar days of the initial 24-hour report.
- “24-Hour notification, 10 Calendar Days” - The SAE must initially be reported via CTEP-AERS within 24 hours of learning of the SAE, followed by a complete expedited report within 10 calendar days of the initial 24-hour report.

SAEs that occur more than 30 days after the last administration of investigational agent/intervention and have an attribution of possible, probable, or definite require reporting as follows:

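### Overall survival is to be summarised by a Kaplan-Meier median, but follow-up stops 30 days after patients leave treatment or study, so most deaths would go unseen and the censoring is tied to prognosis

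*Combined protocol and SAP*

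**What the plan says.** **Endpoint.** Objective 1.3.2 is to determine OS. Section 9.1 is explicit that deaths after treatment count: "OS is defined as the time from initiation of therapy to death from any cause". Section 9.4 gives the analysis: "Survival will initially be modeled using Kaplan-Meier methods, resulting in median survival times with 95% CI, assuming sufficient events have occurred".

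**Follow-up.** Section 6.5: "Patients will be followed for 30 days after removal from study or until death, whichever occurs first". Section 6.1, for the expansion cohort: "Patients will be followed for 30 days after completion of therapy unless treatment related toxicities have not resolved to grade 1". Section 6.2 repeats this: "Patients will be followed for 30 days after completion of therapy unless treatment-related toxicities have not resolved to grade 1". Each of these sections extends the period only for unresolved toxicity or adverse events.

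**What ends therapy.** Section 6.4 lists, among other reasons, disease progression, clinical progression, intercurrent illness, and changes in condition that "render the patient unacceptable for further treatment in the judgment of the investigator".

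**Other routes by which a death could be recorded.** The Study Calendar (11.1) ends with an off-study evaluation and has no vital-status row. Imaging stops at progression, and the 28-day check in footnote m applies only after an abnormal ECG. Section 10.3.2 says "A death on study requires both routine and expedited reporting, regardless of causality", but beyond the window it covers only "SAEs that occur more than 30 days after the last administration of investigational agent/intervention and have an attribution of possible, probable, or definite".

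**The concern.** OS needs deaths to be ascertained well after treatment ends. The follow-up rule stops looking about a month after it ends. Two problems follow.

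- **Few deaths are seen.** A patient who stops at progression and dies some months later contributes a censored time.
- **The censoring is informative.** Kaplan-Meier assumes that a patient censored at a given time has the same outlook as those still followed. Here the censoring time is set by leaving treatment, commonly for progression or deterioration, so the assumption fails by design. The condition in Section 9.4 about sufficient events concerns the number of deaths and does nothing about this.

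At stake is the OS estimate for objective 1.3.2. The median may not be estimable, and a reported value could mislead a reader comparing it with other data.

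**Working it through.** The documents give no event count, precision or power for OS, so there is no figure of theirs to reproduce. The check has two parts.

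**1. Is there any later source of death dates?**

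| Place | What it provides | Captures deaths from disease after 30 days? |
|---|---|---|
| 6.1, 6.2, 6.5 | 30 days, longer only for toxicity or AEs | No |
| 11.1 calendar | Off-study visit; imaging until progression | No |
| 10.3.2 | Beyond 30 days, only treatment-attributed SAEs | No |
| 12.1.4.3 note | Effort to document progression after stopping | No, progression only |
| 13.2.2 | End of Study form, summary of endpoints not otherwise captured | No death dates specified |

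No OS censoring rule or data cut-off is stated.

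**2. How much is lost?**

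Assumptions, because the documents give no post-treatment survival:
- Median time to stopping therapy: 3, 6 or 10.1 months. The ends are the median PFS figures of 3.0 and 10.1 months in Section 2.2.2.3.3; neither is this trial's population.
- Median post-treatment survival *b*: 3, 6, 9, 12 or 18 months.
- Share dying on therapy *p*: 0, 10 or 20%.
- Exponential times, with stopping time and later survival independent.
- The 30 days (0.986 month) start when therapy stops.

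This gives 3 × 5 × 3 = 45 scenarios. Sample sizes are 16 (6 + 10 at the RP2D, Section 9.2) and 22 (12 treated in escalation, Section 2.3, plus 10). The documents do not name the OS population.

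*Share of deaths unseen* = (1 − p) × 2^(−0.986/b)
- Smallest (b = 3, p = 20%): 0.8 × 2^(−0.329) = 0.637
- Largest (b = 18, p = 0): 2^(−0.0548) = 0.963

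*Expected deaths observed, n = 16*: 16 × (1 − 0.963) = 0.6 to 16 × (1 − 0.637) = 5.8.

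*If removal from study comes 3 months after stopping therapy*: (1 − p) × 2^(−3.986/b), which runs from 0.319 to 0.858.

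*Does risk change at censoring?* The monthly hazard of death is p × ln 2 / (stopping median) on therapy and ln 2 / b afterwards. The largest on-therapy value is 0.2 × 0.693/3 = 0.046. The post-treatment values are 0.231, 0.116, 0.077, 0.058 and 0.039 for b = 3, 6, 9, 12 and 18. Only one scenario (stopping 3, b = 18, p = 20%) has a lower hazard after stopping; in the other 44 it rises.

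*Simulated Kaplan-Meier results*, 10,000 trials per scenario (range ends move by a point or two between runs):

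| | n = 16 | n = 22 |
|---|---|---|
| Median not reached | 19–93% | 14–94% |
| Mean deaths observed | 0.6–5.8 | 0.8–8.0 |

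When the median is reached at n = 16, at most two patients are still at risk in 33–97% of cases, and the value is within 25% of the truth in 7–53%.

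*Direction of error*, n = 16, p = 0, typical reached median against truth:

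| Stopping / post-treatment median (months) | Reached | True |
|---|---|---|
| 6 / 3 | about 20 | 10.6 |
| 3 / 6 | about 12 | 10.6 |
| 3 / 18 | about 12.5 | 22.7 |

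The true value for the first two rows can be checked by hand. Survival is 2u − u² with u = 2^(−t/6); setting this to 0.5 gives u = 0.293 and t = 10.6 months. In the last row few trials reach a median at all, and those that do rest on early deaths, which is why the value is low.

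**The case against.** - **Small samples are noisy anyway.** With every death observed, the median at n = 16 falls within 25% of the truth in only about 50–73% of trials. This stands: part of the 7–53% is noise that longer follow-up cannot remove, and the 25% tolerance is a choice made for illustration. It does not explain the unseen deaths or the informative censoring.
- **The clock in Section 6.5 is removal from study, which may be later.** Section 6.4 records therapy discontinuation and study removal separately, and imaging continues until progression. With a 3-month delay at n = 16, the median is not reached in about 0–78% of trials, 2.3–10.9 deaths are observed on average, and reached medians are within 25% of the truth in 27–56%. This softens the result, but 32–86% of deaths are still unseen. The calendar also speaks of removing patients from study for progression, which favours the short clock for them.
- **Section 6.4 does not rank the reasons for stopping**, and telaglenastat supply ends on 2/28/25 for a reason unrelated to prognosis. Fair: how often stopping reflects prognosis is a clinical expectation, not a documented frequency.
- **Section 9.4 is conditional on sufficient events.** That would often withhold the median, but would not correct one that is reported.
- **OS is minor here**: exploratory in Section 1.3, secondary in 9.1 and unpowered. This stands and limits the weight of the point.
- **Case report forms and schema figures are not visible**, so the absence of vital-status capture is shown for the available text only.

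**Conclusion.** The concern holds. As written, OS counts deaths from any cause while follow-up ends 30 days after therapy or study removal, and no later vital-status collection was found. Under the stated assumptions 64–96% of deaths go unseen, or 32–86% if removal from study trails therapy by 3 months. A median would often not be reached. When reached it is unreliable, and its direction of error cannot be predicted. The percentages depend on assumed survival times; the conflict between endpoint and follow-up does not. The safety and RP2D conclusion is untouched, so this is a lower-priority correction that should still be made before OS is analysed.

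**What to change.** Choose one:

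- **(a)** Withdraw the OS median from objective 1.3.2 and Sections 9.1 and 9.4, and report only deaths within the follow-up window. Cost: text changes.
- **(b)** Add to Section 6.5 and the Study Calendar periodic vital-status collection by chart review or telephone, recording date of death or date last known alive, to a stated data cut-off, with OS censored at the date last known alive. Cost: periodic checks on at most 28 patients (the maximum in Section 9.2). The Summary of Changes says accrual is closed, so some patients may already be past the 30-day window; chart access, re-contact or added consent may be needed.

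In either case, reconcile the starting point of the 30 days (completion of therapy in 6.1 and 6.2, removal from study in 6.5), and give PFS and OS one endpoint level (exploratory in 1.3, secondary in 9.1).
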